Autologous fat grafting or lipo injection containing stromal vascular fraction (SVF) acts like ideal soft tissue filler for facial filling and rejuvenation.⁽⁴⁾ It leads to progressive improvement of the skin texture, elasticity, and color over a few

months, therefore adipose tissue seems to be not only a simple filler but also a dynamic filler with two types of different and supplementary effects, the volumetric effect and the regenerative effect.⁽⁷⁾

Recently, adult stem cells such as mesenchymal stem cells (MSCs) have been used in variable dermatologic conditions due to its regenerative properties such as wound healing, rejuvenation, acne scar and hair fall treatment. Different types of MSCs could be derived from different tissues as for example; bone marrow stem cells (BMSCs), adipose tissue-derived stem cells (ADSCs), and skin-derived stem cells (SDSCs).⁽⁸⁾

Adipose tissue derived stem cells are currently favorable compared to other types of adult stem cells as the procedure is easy, safe with minimal donor site morbidity. The process of obtaining a considerable amount of adipose tissues sufficient to use in skin regeneration is highly appealing due to its relative availability and accessibility. They secrete variable growth factors that affect surrounding environment as vascular endothelial growth factor (VEGF), platelet derived growth factor (PDGF), insulin like growth factors (IGF) and others.⁽⁹⁾

Cell assisted lipotransfer (CAL) is a technique that combines aspirated fat with concentrated ADSCs in the stromal vascular fraction (SVF) of the lipoaspirate. This technique could enhance the survival rate of the transplanted fat and leads to better cosmetic improvement.⁽⁸⁾

AIM OF THE WORK

The aim of this work is to evaluate the effect of Adipose Derived Stem Cells on Survival of Fat as Filler

PATIENTS

The current study will be carried out on 15 healthy female participants recruited from the Outpatient Clinic of the Dermatology Department of Alexandria Main university hospital.

Inclusion criteria:

1. Clinically diagnosed facial skin aging.
2. Glogau photoaging score II and III.
3. Body mass index ≥ 20 with adequate abdominal or other subcutaneous adipose tissue accessible for lipoaspiration.

Exclusion criteria:

1. History of keloid formation.
2. Any coincidental chronic illness (e.g. metabolic, autoimmune or endocrinial) or malignancy.
3. Any bleeding or coagulation disorder or recent use of anticoagulant therapy.
4. Active infection.
5. History of any previous aesthetic procedure on the face within the past 6 months.
6. History of intake of anti-aging systemic or topical medications within the previous 3 months.

An informed consent for both participations in the study and photography will be taken from all participants prior to the onset of the study after full explanation of the procedure and its follow up steps. Patients will have to sign to committing to the study protocol, using sun protection, and abstaining from using or doing any anti-ageing steps during the study period.

METHODS

All participants will be subjected to:

1. Full history taking including personal, family, medical and drug history.
2. History of any previous aesthetic procedures on the face.
3. BMI calculation.⁽¹⁰⁾
4. Baseline assessment of facial skin ageing will be done using the following techniques:
 - Base line standardized digital photography of the face before the procedure and in each follow up visit.
 - Assessment of degree of improvement using Hollowness severity rating scale: 0: no visible hollowness, 1: mild Hollowness, 2: moderate H, 3: severe Hollowness on serial photography.
 - Assessment of trans-epidermal water loss (TEWL) and skin hydration using noninvasive probe (Dermal measurement system EDS12, UK) on both temple regions of the head.⁽¹³⁾
 - Measurement of epidermal, dermal and hypodermal thickness using UBM (Ultrasound Bio microscopy) on both temple regions of the head.⁽¹⁴⁾

Lipoaspiration for preparation of ADSC will be done according to the following technique:⁽⁷⁾

Under local anesthesia using strict aseptic technique, a small incision will be done in the lateral aspect of the thigh or lower abdomen, through which the infiltration cannula will be introduced to inject the local anesthetic solution using the wet technique. This will be followed 15 minutes later by lipo-aspiration of (50 ml fat) using a blunt tipped cannula under the negative suction pressure of a 60 ml syringe.

- Autologous adipose tissue derived stem cells (At-ADSCs) will be separated from the lipo-aspirate using enzymatic digestion and

differential centrifugation in the Center of Excellence for Research in Regenerative Medicine and its Application (CERRMA), Alexandria Faculty of Medicine.

- Viability of collected cells will be checked using trypan blue stain.⁽¹⁵⁾ Characterization of the isolated ADSCs population will be performed by flow cytometry to check for specific cell surface CD antigens (CD 90 and CD 34) in three independent cases in triplet.⁽⁷⁾

Aspiration of 75 ml of fat followed by preparation of At-ADSCs from 25 ml.

- One temporal region is randomly selected as control to receive the required volume of fat via subcutaneous injection using blunt cannula. The other side receive equal volume of fat enriched with ADSCs in SVF.

Follow up and evaluation:

- Early assessment of trans-epidermal water loss (TEWL) and skin hydration will be carried out a week after the procedure.
- All participants will be followed up six months after the procedure. Follow up will entail using the same base line assessment steps to detect the effects of treatment. Side effects reported by the participants will be recorded.
- Assessment of the participants and the photos will be carried out by a blinded investigator to the half treated and the before versus after photos.
- A visual analog scale,⁽¹⁶⁾ will be used to assess participants' satisfaction by the treatment

ETHICS OF RESEARCH

Research on human or human products:

- Prospective study: informed consent will be taken from patients. In case of incompetent patients the informed consent will be taken from the guardians.
- Retrospective study: confidentiality of records will be considered.
- DNA/genomic material: informed consent for DNA / genomic test and for research will be taken from patients. No further test will be carried out except with further approval of committee and patients. If the samples will travel outside Egypt the researcher will be responsible for transportation and security approval.
- All drugs used in the research are approved by the Egyptian Ministry of Health.

Research on animal:

- The animal species are appropriate for the test.
- After test, if animal will suffer, it will be euthanized and properly disposed.
- After operation, it will have a proper postoperative care.

RESULTS

The results obtained will be tabulated, statistically analyzed and findings will be illustrated using tables and figures.

DISCUSSION

The results obtained will be discussed in view of achievement of the aim of the work and compared with other findings in literature.

REFERENCES

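### The single six-month washout admits women with older fat or filler in the temple, the tissue where graft survival is read; the likely harm is noise, not systematic bias

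*Protocol*

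**What the plan says.** Under PATIENTS, Exclusion criteria, item 5 removes women with "History of any previous aesthetic procedure on the face within the past 6 months". It does not distinguish a fat graft or filler from any other facial procedure, and no other criterion covers older ones.

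Under METHODS, item 2 takes a "History of any previous aesthetic procedures on the face" with no time limit. Nothing follows from an older entry: it leads to no exclusion, stratification or adjustment.

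The objective under AIM OF THE WORK is stated as "The aim of this work is to evaluate the effect of Adipose Derived Stem Cells on Survival of Fat as Filler". The assessments that bear on it are:

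- a hollowness grade from 0 to 3 on serial photographs;
- ultrasound: "Measurement of epidermal, dermal and hypodermal thickness using UBM (Ultrasound Bio microscopy) on both temple regions of the head".

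Follow up and evaluation sets the late visit: "All participants will be followed up six months after the procedure". It adds: "Follow up will entail using the same base line assessment steps to detect the effects of treatment".

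The comparison is within each woman, with the side allocated by chance: "One temporal region is randomly selected as control to receive the required volume of fat via subcutaneous injection using blunt cannula". The sample is 15 women.

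**The concern.** The washout and the follow-up are the same length. A six-month visit is informative about fat survival only if grafted fat can still be present then. Yet item 5 treats six months as long enough to clear any earlier procedure, including the kind under test. An eligible woman could enter with a temple graft slightly more than six months old, about the age the study graft will have when its own survival is judged.

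Ultrasound gives a thickness for each layer. The Protocol describes no way of dividing hypodermal thickness between old and new material. If old material is present and changes, the change is attributed to the study graft. A temple that was filled earlier may also start with little or no visible hollowness, and no inclusion criterion requires any. At stake are the precision of the comparison between sides in a very small sample and the meaning of any survival figure reported for each side.

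**Working it through.** The Protocol gives no power, alpha, effect size or standard deviation, so there is no stated figure to reproduce. The check has two parts: what cancels, and how large the remainder could be.

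**What cancels.** For one temple, let T be native thickness (taken as constant), O0 and O6 the old material at baseline and six months, L = O0 − O6 its loss, and G the surviving study graft. E is the enriched side and C the control side.

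- Baseline reading: T + O0
- Six-month reading: T + O6 + G
- Change from baseline: G − L
- Difference between sides in change: (G_E − G_C) − (L_E − L_C)
- Difference between sides in six-month values alone: (G_E − G_C) + (T_E − T_C) + (O6_E − O6_C)

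Four results follow.

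1. If old material is stable (L = 0), it drops out of the change from baseline.
2. If it is lost equally on both sides, it drops out of the difference between sides, but the change on each side understates G by L.
3. If it is lost unequally, L_E − L_C stays in that woman's difference. With the side randomised and the loss unaffected by the enrichment, its expectation is zero, so it adds variance and not bias.
4. Old material enters as such, through O6_E − O6_C, only if six-month values are compared without baseline.

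**How large the remainder could be.** Inputs: n = 15 pairs, from the Protocol. The number k of affected women and the standard deviation s of the side difference in loss, in units of the standard deviation of the paired difference, are assumptions.

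SE inflation = √(1 + (k/15)·s²)

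| k | s = 0.5 | s = 1.0 |
|---|---|---|
| 0 | 1.000 | 1.000 |
| 1 | √1.0167 = 1.008 | √1.0667 = 1.033 |
| 3 | √1.05 = 1.025 | √1.20 = 1.095 |
| 5 | √1.0833 = 1.041 | √1.3333 = 1.155 |

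A simulation of 15 pairs with no true effect (100,000 runs per row) agreed, with inflation of 1.005 and 1.032 for k = 1, 1.023 and 1.095 for k = 3, and 1.038 and 1.153 for k = 5. Mean bias was at most 0.002 standard deviations throughout.

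**A single realised trial.** If old one-sided material loses d mm in each of k women, all with the same study arm affected, the mean difference shifts by k·d/15. Again, k and d are assumed.

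- k = 1: 1/15 = 0.067 mm (d = 1); 2/15 = 0.133 mm (d = 2)
- k = 2: 2/15 = 0.133 mm (d = 1); 4/15 = 0.267 mm (d = 2)

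For two such women, randomisation makes it equally likely that opposite arms are affected, and equal losses then offset exactly. Without a standard deviation or target effect in the Protocol, none of these shifts can be called important or trivial.

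**Hollowness.** The grade is bounded at 0. A temple that starts at 0 cannot improve, and one that starts at 1 can improve by one grade only. Subtracting the baseline does not restore the lost range.

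**The case against.** The strongest reply is that the design already deals with most of this. Both temples are measured by ultrasound before the procedure and again at six months, the comparison is within each woman, and the side is randomised. Stable residue and equal bilateral loss therefore leave the comparison between sides intact, and unequal loss only widens it slightly. Prior procedures are recorded, so affected women could be identified in a sensitivity analysis. Whether change from baseline is analysed is a matter for the SAP, which is not shown, so the Protocol's silence on it is not a fault.

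All of that stands, and it rules out several stronger readings.

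- A reader might infer that old filler will be counted as surviving study fat. That follows only if baseline is ignored, and nothing in the Protocol says it will be.
- A reader might infer that old material is still resorbing. The six-month visit implies that graft may be present at that age, not that it goes on shrinking afterwards. The Protocol does not address this.
- A reader might take the introductory text as crediting fat with a lasting effect. It says "adipose tissue seems to be not only a simple filler but also a dynamic filler with two types of different and supplementary effects", which concerns kinds of effect and not duration, and it describes skin improvement over a few months.
- A reader might infer from the growth factors described in the introductory text that enrichment also preserves old fat, which randomisation would not remove. The Protocol does not show this, and the conclusion here does not rest on it.
- No primary endpoint is named. That survival is judged at six months is inferred from the aim and the visit schedule.

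The reply does not remove the eligibility gap. Item 5 is a stated rule, it fits poorly with the trial's premise, and neither baseline subtraction nor randomisation repairs survival per side when old material changes, or the limited range of the hollowness grade.

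**Conclusion.** The point holds in limited form: women with older fat, SVF/ADSC or filler in the temple are eligible, and six months is not a convincing clearance period in a trial that looks for fat at six months.

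The consequences are modest. The comparison between sides is not systematically biased, provided change from baseline is used and enrichment does not itself alter the loss of old material. It may be noisier: about 1.01 to 1.03 times the standard error with one of 15 women affected, and 1.04 to 1.15 with five, for side differences in loss of 0.5 to 1.0 standard deviations. Chance imbalance remains possible in 15 pairs. Survival per side would be misread where old material changes, and the hollowness scale may have little room to show benefit.

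The true size cannot be given, because the Protocol states neither how often earlier temple treatment occurs nor how much material remains. This is an inexpensive improvement to eligibility and does not invalidate the design.

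**What to change.** Keep the six-month rule in Exclusion item 5 for other facial procedures, and add: or any previous fat graft, SVF/ADSC injection, filler or implant in either temporal region, at any time. Apply it from the history already taken under METHODS, item 2. State in the Protocol or SAP that thickness and hollowness are analysed as change from baseline for each temple.

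With no affected women (k = 0), the SE inflation from this source is 1.00.

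The cost is one clause on eligibility and one sentence on analysis, with no new assessment. A few candidates would be turned away, which may slow recruitment of the 15 slightly. A lighter alternative is to admit these women, use change from baseline and repeat the analysis without them. That settles direct counting, but it leaves the limited hollowness range in the main analysis and makes an already small sample smaller in the sensitivity analysis.

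### Does the equal-volume rule for the two temples mix injected volume with the effect of the cells?

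*Protocol*

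**What the plan says.** The Protocol's aim is to "evaluate the effect of Adipose Derived Stem Cells on Survival of Fat as Filler". Under METHODS, after the description of cell preparation, the allocation rule is: "One temporal region is randomly selected as control to receive the required volume of fat via subcutaneous injection using blunt cannula". The next sentence reads: "The other side receive equal volume of fat enriched with ADSCs in SVF". The Protocol gives no injected volume in ml, no volume for the cell preparation and no vehicle for the control temple.

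Two outcomes depend on volume. One is ultrasound: "Measurement of epidermal, dermal and hypodermal thickness using UBM (Ultrasound Bio microscopy) on both temple regions of the head". The other is a photographic grade from 0 to 3: "Assessment of degree of improvement using Hollowness severity rating scale". Both are baseline measures, and Follow up and evaluation repeats the baseline steps at six months. The one-week visit is narrower: "Early assessment of trans-epidermal water loss (TEWL) and skin hydration will be carried out a week after the procedure".

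**The concern.** Fat survival is retained fat divided by fat placed, so the amount placed is the denominator of the trial's question. The control temple receives fat alone and the other receives fat plus a preparation that has some volume. Matching the total leaves less fat on the enriched side; matching the fat leaves more total volume there. Randomising which temple is the control does not help, because the imbalance always follows the enriched side. No thickness reading is planned soon after injection that could serve as a substitute denominator.

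At stake is the claim that the two temples differ only in the cells. If total volume is matched and the preparation is a sizeable share of it, a real survival benefit could be diluted or hidden. If fat is matched, the enriched side starts out fuller, which might be read as a benefit.

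**Working it through.** **Inputs from the Protocol.** The aim is fat survival. The control is plain fat. The other temple gets an equal volume of enriched fat. Thickness and hollowness are measured at baseline and six months. The Protocol states no volume, effect size or SD that bears on the point, so there is no figure of its own to reproduce.

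**Assumptions, none from the Protocol.** Let V be the fat volume on the control side and f the preparation volume as a fraction of V, taken from 1% to 30%. Let R be the true ratio of fat retention, enriched to control. Control retention is set at 50% for illustration.

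**If fat is matched.** Each side receives V of fat. Total volume on the enriched side is (1 + f)V, or 1.01 to 1.30 times control at injection. If the carrier fluid is absorbed by six months, the expected ratio of retained fat is R, with no bias. The larger early fill has little chance to enter the results, since the one-week visit names only water loss and hydration.

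**If total volume is matched.** The enriched side receives (1 − f)V of fat, so the expected ratio of retained fat is R(1 − f). The enriched side equals control when its retention is 0.5/(1 − f).

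| f | Fat placed, enriched/control | Break-even retention | Benefit hidden (points) | Apparent ratio if R = 1.25 |
|---|---|---|---|---|
| 1% | 0.99 | 50.5% | 0.5 | 1.24 |
| 5% | 0.95 | 52.6% | 2.6 | 1.19 |
| 10% | 0.90 | 55.6% | 5.6 | 1.13 |
| 20% | 0.80 | 62.5% | 12.5 | 1.00 |
| 30% | 0.70 | 71.4% | 21.4 | 0.88 |

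For example, at f = 20%, 0.5/0.80 = 0.625 and 1.25 × 0.80 = 1.00. Every factor (1 − f) is below 1, so this bias always runs against the cells.

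**Which reading the text supports.** In the control sentence the measured quantity is the volume of fat. The next sentence says the volume is equal and again names fat, with the enrichment describing that fat. Taken together they most naturally match the fat. The wording does not exclude the other reading.

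**Where f is likely to lie.** The introduction describes cell-assisted transfer as fat combined with concentrated cells, and METHODS obtains them by digestion and differential centrifugation. A small added volume is therefore plausible, though not stated. The aspirate figures do not settle it: 75 − 25 = 50 ml of unprocessed fat limits the fat available but says nothing about the volume of the preparation. (METHODS also gives a 50 ml aspirate; those passages must be reconciled, but that is a separate matter.)

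**Whether normalising would help.** Hypodermal gain per ml of fat assumes that thickness at a measured site is proportional to volume injected, which nothing in the Protocol supports. It cannot be applied to a 0 to 3 grade. It also leaves total volume unequal, so the sides would still not differ in cells alone.

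**The case for a change.** The strongest contrary case is that what is injected defines the intervention, so it belongs in the protocol and cannot be left to the analysis plan. The Protocol sets no upper limit on the preparation's share and does not say that either volume will be recorded. A reader might therefore be unable to show afterwards that the imbalance was small, and operators could apply the rule differently from one participant to the next. With 15 participants there is little precision to spare.

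Some of this stands. The matched quantity is not defined beyond its wording, the two volumes cannot both be exactly equal, and randomisation does not cure the difference. A clarifying phrase and a note of the volumes would do no harm.

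It does not show a flaw in the comparison. The rule asks for equality and prescribes no unequal quantity, and the two sentences do not contradict each other. The sizeable figures need both the less natural reading and a large assumed share. A cell-free vehicle on the control side would equalise both volumes, but the comparator would then no longer be plain fat. That is a trade-off, not a correction.

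**Conclusion.** The concern identifies a missing detail, not an error that calls for a change. On the natural reading fat is equal on the two sides and the six-month contrast estimates the retention ratio R without bias, provided the carrier fluid has been absorbed by then. If some persisted, the bias would favour the cells; the Protocol gives no ground for assuming so. On the other reading the loss is the factor (1 − f): about 1% for a small concentrate and 20% for a bulky suspension. Its direction is against the cells, so a positive finding would survive it, while a null finding would need the share to be known.

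These sizes rest on a share the Protocol does not give and on an assumed 50% control retention. Anyone following the rule has to measure out a volume for each temple, so the team must settle what is matched when the syringes are filled. It can report this with the results. Per-ml thickness would be at most a sensitivity analysis.

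### Side effects are collected only by a passive rule: no questioning or safety examination is planned at either visit, and recording by temple or donor site is not specified

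*Protocol*

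**What the plan says.** All the relevant text is in the Protocol.

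- **Safety data** (METHODS, Follow up and evaluation): "Side effects reported by the participants will be recorded". This sentence closes the six-month bullet and has no timing of its own. It does not mention questioning, examination, site, onset or resolution.
- **One-week visit** (same section): "Early assessment of trans-epidermal water loss (TEWL) and skin hydration will be carried out a week after the procedure". Side effects are not listed.
- **Six-month visit** (same section): "All participants will be followed up six months after the procedure". Its content is the set of baseline steps (METHODS, item 4): photography, the hollowness scale, water loss and hydration, and ultrasound thickness.
- **Design** (METHODS): one temple, chosen at random, is the control and receives plain fat. For the opposite temple the text reads: "The other side receive equal volume of fat enriched with ADSCs in SVF". The sample is fixed under PATIENTS: "The current study will be carried out on 15 healthy female participants".
- **Harvest site** (METHODS, Lipoaspiration): "a small incision will be done in the lateral aspect of the thigh or lower abdomen".
- **Measures that do name the site** (METHODS, item 4): water loss, hydration and ultrasound thickness are each to be measured at both temples.
- **Photography and blinding:** facial photographs are required before the procedure and at every follow-up visit (METHODS, item 4). A blinded investigator assesses the participants and the photographs (Follow up and evaluation).

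**The concern.** A rule that records what participants report depends on each woman noticing an event, thinking it worth mentioning and mentioning it. Events that resolve early, seem minor or lie at the harvest site are the ones most easily lost. The protocol already brings every participant to the clinic at one week and measures both temples, but plans no side-effect question or inspection there.

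The second issue is attribution. Treatment differs only by side within each woman, and there is a third wound at the thigh or abdomen. An event written down without its site cannot be placed with enriched fat, plain fat or the harvest. The split-face design is well suited to describing whether the cell preparation changes local side effects, and that opportunity depends on the site being recorded.

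This is a data-collection rule. A statistical analysis plan can decide how to tabulate events, but it cannot restore a site or date that was never collected.

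**Working it through.** The protocol states no safety figure, so there is none to reproduce. The check is mainly a comparison of the text, with two calculations for scale.

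**1. What each planned contact collects on safety**

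| Contact | Listed content | Planned questions on side effects | Planned safety examination |
|---|---|---|---|
| One week | water loss, hydration (photographs too, if this counts as a follow-up visit) | none | none |
| Six months | photographs, hollowness scale, water loss and hydration, ultrasound thickness, satisfaction scale | none; participant reports are recorded | none |
| Any time | nothing scheduled | none; reports are not excluded | none |

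The donor site is not examined at any contact. The temples are measured and photographed, but to assess ageing and treatment effect.

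**2. What attribution needs.** Each of the 15 women has three possible local sites: the enriched temple, the control temple and the harvest incision. A local event can be assigned only if its site is written down. The protocol names the site for the probe and ultrasound measurements but not for side effects. Donor-site and systemic events cannot be assigned to a temple under any scheme, so a comparison by side applies to local temple events alone.

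**3. What 15 pairs could support if the side were always recorded.** In a paired comparison only discordant pairs (an event in one temple and not the other) carry information. With m discordant pairs all in one direction, the exact McNemar (sign) test gives two-sided p = 2 × 0.5^m:

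- m = 5: 2 × 0.03125 = 0.0625
- m = 6: 2 × 0.015625 = 0.031

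So at least 6 of the 15 women would need an event in the same treatment's temple only, with none the other way round, to reach p<0.05. The comparison is therefore descriptive.

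**4. Illustration of under-capture (assumed inputs).** The documents give neither an event rate nor the share of events that participants would report. Let p be the assumed proportion of women with an early event and r the assumed share that gets recorded. The chance that at least one event is recorded among 15 is 1 − (1 − p·r)^15:

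| Assumed p | r = 1 | r = 0.75 | r = 0.5 | r = 0.25 |
|---|---|---|---|---|
| 10% | 79% | 69% | 54% | 32% |
| 20% | 96% | 91% | 79% | 54% |

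For example, with p = 10% and r = 0.5: 1 − 0.95^15 = 0.54. This shows how the chance of seeing any event falls with incomplete capture. It does not estimate what would happen in this trial.

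**The case against.** The case on the other side has real force.

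- **Timing.** The side-effect sentence has no time limit; it merely sits in the six-month bullet. A reader might infer that early events would be known only through recall about 25 weeks later. The text does not say so: a report made at one week or between visits is not excluded.
- **Photographs.** The one-week visit is not clearly confined to the probe measurements. If it counts as a follow-up visit, the face is photographed then, which would give a dated, side-specific record of visible temple events. This stands. Such photographs would not show symptoms or the donor site, and they are not planned as a safety review.
- **Side.** The protocol is silent on side; it does not say that side will be omitted. A case report form not shown may record it, and a woman reporting a lump would probably say where it is. A reader might infer that none of the 15 pairs could support a safety comparison. That would follow only if the side were never written down, which the document does not state.
- **Objective.** The stated aim is fat survival, and no comparative safety claim is planned. This limits the weight of the point.
- **The zero-event bound.** One might note that 0 events in 15 leaves a one-sided 95% upper bound of 1 − 0.05^(1/15) = 18%. This depends only on the sample size and is the same under perfect capture, so it does not measure the weakness of the rule.

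What remains is that the stated method is passive, and that following it exactly would still leave no planned question and no planned safety inspection at either visit.

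**Conclusion.** The point holds in a limited form. The only safety rule is passive, no active capture is planned at one week or six months, and the site of an event is not specified. Symptoms, donor-site events and unreported events can be missed, and any event recorded without its site could not be assigned to enriched or plain fat.

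The documents do not support saying that early events will be lost or that the two treatments cannot be compared for safety. The conclusion assumes that no unseen form or procedure already adds fixed questions, inspection and site. If one does, the protocol need only say so.

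The loss cannot be quantified from the documents. Safety is outside the stated aim and 15 pairs allow only description, so this is a cheap improvement that does not threaten the trial's main conclusion.

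**What to change.** In Follow up and evaluation, replace the single sentence with a short procedure for the two visits already planned, at one week and six months:

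1. Ask every participant the same fixed set of side-effect questions.
2. Inspect the right temple, the left temple and the donor site separately. Keep whoever assesses the temples blinded to which side received enriched fat.
3. Record site, onset and resolution for each event, and continue to record reports made between visits.
4. Report local events descriptively by enriched versus control temple, paired within participant. List donor-site and systemic events separately.
5. State that no formal safety claim will be made from 15 pairs.

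**Cost:** one short form and a few minutes per visit, with no added visit. More minor events will be recorded. The protocol does not say whether the blinded investigator attends at one week or will see the donor site, so the sponsor should confirm who does each inspection.
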